### SUMMARY OF CHANGES

The following is a list of significant protocol changes from v2.0 dated 12 June 2015 to v2.1 dated 27 April 2016. All other changes are administrative and do not significantly affect the safety of subjects, study scope, or scientific quality of the protocol.

1. The duration of the study changed from 3 years from last study treatment/EP to 36 weeks. This change still fulfills the study primary objectives, which include safety, tolerability and immunogenicity in subjects with cervical cancer and received INO-3112/EP treatment.
2. Updated the estimated number of Study Centers
3. Number of subjects to be enrolled in the study changed from 30 to 10 subjects. This is mainly due to study primary objectives and the challenge in trial operation/enrollment.
4. Specified in section 6.1.1 and 6.7 that the subjects with HPV-16 and/or HPV-18 positive from In-situ hybridization (ISH) or polymerase chain reaction (PCR) assays will be eligible for the study.
5. Added the option to conduct Weeks 2, 6, 8 and 10 visits as phone visit or in-person office visit. This change intends to be more convenient for study subjects.
6. Eliminated collection of the blood samples at Weeks 2, 4, 6, 10 and 14.
7. The medical monitor and associated contact information was updated to reflect a resourcing update by the Sponsor. All responsibilities of the updated medical monitor will remain the same.

---

PROTOCOL ACKNOWLEDGEMENT

I have read this Protocol and agree that it contains all necessary details for carrying out the study described. I understand that it must be reviewed by the Institutional Review Board or Independent Ethics Committee overseeing the conduct of the study and approved or given favorable opinion before implementation.

The signature of the Principal Investigator and Sponsor below constitute their approval of this protocol and proved the necessary assurances that this study will be conducted according to The Declaration of Helsinki, GCP, ICH guidelines, local legal and regulatory regulations as well as to all stipulations of the protocol in both the clinical and administrative sections, including statements regarding confidentiality.

\_\_\_\_\_  
Investigator's printed name and signature

\_\_\_\_\_  
Date

\_\_\_\_\_  
[REDACTED], MD  
Medical Monitor

\_\_\_\_\_  
Date

*Protocol Number: HPV-004*

*Site Number:*

*Version Number/Version Date: v2.1/27 April 2016*

---

## CLINICAL PROTOCOL SYNOPSIS

Title of Study: Phase I/IIA, Open-Label, Safety, Tolerability, and Immunogenicity Study of INO-3112 Delivered by Electroporation (EP) in Women with Cervical Cancer after Chemoradiation for Newly Diagnosed Disease or Therapy for Recurrent and/or Persistent Disease
Estimated Number of Study Centers and Countries/Regions: 2 sites (United States)
Number of Subjects : Approximately 10 subjects
Study Phase: I/IIa
Research Hypothesis: Immunotherapy with INO-3112 delivered by intramuscular (IM) injection followed by EP with CELLECTRA ® -5P will be immunogenic and well tolerated in women with newly diagnosed, inoperable cervical cancer associated with HPV-16 and/or HPV-18 after completion of standard chemoradiation therapy with curative intent (Cohort 1) or in women with persistent and/or recurrent cervical cancer associated with HPV-16 and/or HPV-18 following salvage therapy (Cohort 2) and will not be associated with any significant increased toxicity compared to that expected/reported with “standard” therapy alone.
Primary Objective: 

• Evaluate the safety and tolerability of immunotherapy with INO-3112 when delivered IM followed by EP with CELLECTRA®-5P in women with newly diagnosed, inoperable cervical cancer associated with HPV-16 and/or HPV-18 after completion of standard chemoradiation therapy with curative intent (Cohort 1) or in women with persistent and/or recurrent cervical cancer associated with HPV-16 and/or HPV-18 following salvage therapy (Cohort 2) compared to that expected/reported with “standard” therapy alone.

Secondary Objective: 

• Evaluate the cellular and humoral immune responses to immunotherapy with INO-3112 delivered IM followed by EP with CELLECTRA®-5P in women with newly diagnosed, inoperable cervical cancer associated with HPV-16 and/or HPV-18 after completion of standard chemoradiation therapy with curative intent (Cohort 1) or in women with persistent and/or recurrent cervical cancer associated with HPV-16 and/or HPV-18 following salvage therapy (Cohort 2).

Exploratory Objective: 

• Evaluate clinical responses (disease-free survival and progression-free survival) following treatment with INO-3112 delivered intramuscularly followed by EP with CELLECTRA®-5P in women with newly diagnosed, inoperable cervical cancer associated with HPV-16 and/or HPV-18 after completion of standard chemoradiation therapy with curative intent (Cohort 1) or in women with persistent and/or recurrent cervical cancer associated with HPV-16 and/or HPV-18 following salvage therapy (Cohort 2).

**Study Design:** This is a Phase I/IIa, open-label study to evaluate the safety, tolerability, and immunogenicity of INO-3112 [6 mg of VGX-3100 (2 separate DNA plasmids encoding E6 and E7 proteins of HPV 16 and HPV 18) and 1 mg of INO-9012 (DNA plasmid encoding human interleukin 12)] delivered IM by EP in approximately 10 female subjects with biopsy-proven, Stage IB-IVB inoperable invasive cervical carcinoma associated with HPV-16 and/or HPV-18 who have completed treatment with standard chemoradiation therapy with curative intent (Cohort 1) or in subjects with persistent and/or recurrent cervical cancer associated with HPV-16 and/or HPV-18 following salvage therapy (Cohort 2).

Eligible subjects who consent to participate in the study will receive a 1.1 mL IM injection of INO-3112 in the deltoid followed immediately by EP with CELLECTRA®-5P. If the deltoid is not a suitable location, the IM injection should be in the lateral quadriceps followed immediately by EP with CELLECTRA®-5P. All subjects (Cohorts 1 and 2) will receive a 4-dose series of INO-3112. The first study treatment/EP after completion of standard chemoradiation (Cohort 1) or salvage therapy (Cohort 2) will be designated as “Day 0”, the second dose will be administered at Week 4, the third dose at Week 8, and the fourth (final) treatment will be administered at Week 12.

**Cohort 1:**

Cohort 1 will include subjects with biopsy-proven, Stage IB-IVB inoperable, newly diagnosed, invasive cervical carcinoma associated with HPV-16 and/or HPV-18 treated with standard chemoradiation therapy with curative intent.

All subjects in Cohort 1 must receive their first study treatment (Day 0) within 2 weeks after completing a course of standard radiation therapy (external beam and brachytherapy) administered concurrently with platinum based therapy with curative intent. (Refer to Appendix 3: Standard Chemoradiation Guidelines)

**Cohort 2:**

Cohort 2 will include subjects with persistent and/or recurrent cervical carcinoma associated with HPV-16 and/or HPV-18 treated with salvage therapy (chemotherapy and/or radiation therapy).

All subjects in Cohort 2 must receive their first study treatment (Day 0) no sooner than 2 weeks and no later than 4 weeks after completing a course of salvage therapy. If in the investigators opinion, there are no additional salvage therapy options, the subject may be enrolled in Cohort 2 without having received salvage therapy immediately prior to enrollment.

Primary Safety Endpoints:

1. Incidence of adverse events (all, severe [graded per Common Toxicity Criteria for Adverse Events (CTCAE) v4.03], unexpected, serious) classified by system organ class (SOC), preferred term, severity, and relationship to study medication and schedule
2. Injection site reactions including pain, tenderness, erythema and induration at the administration site
3. Rates of acute gastrointestinal, genitourinary, or other chemoradiation side effects above the expected, graded per Acute Radiation Morbidity Scoring Criteria (RTOG)
4. Changes in laboratory parameters from baseline

**Study Design Contd.:**

Secondary Immunologic Endpoints:

1. Antigen-specific cellular immune responses to INO-3112 in blood samples obtained from subjects per study schedule:
  - a. Interferon- $\gamma$  secreting T lymphocytes in PBMC by ELISpot
  - b. Flow Cytometry for T-cell activation, cytolytic phenotype, and memory phenotype in PBMC
2. Antigen-specific humoral responses to HPV-E6 and -E7 by ELISA per study schedule

Exploratory Clinical Endpoints:

1. Changes in standard uptake volume (SUV) on PET/CT scans performed at baseline vs follow-up PET/CT scans obtained at specified time points
2. Evaluation of subjects relative immune competence longitudinally throughout the study starting at the screening visit (for details refer to Section 6.7: Cervical Virologic and Peripheral Blood Immunogenicity Assessment)
3. Changes in cervical histology from the screening biopsy as compared to the week 16 biopsy
4. Local immune responses to INO-3112 in tumor tissue samples obtained at week 16
5. Disease-free survival assessed in accordance with RECIST v1.1 (refer to Appendix 10) as follows:
  - Clinical evaluations for disease response will be conducted at all study visits (as assessed by clinical signs and symptoms of disease progression)
  - A baseline PET/CT scan will be obtained on each subject within 4 weeks prior to Day 0 and then PET/CT scans for disease progression will be obtained for all subjects 3-4 months after Day 0 and 3-5 months thereafter per standard of care/in accordance with local guidelines and institutional practices. Additional PET/CT scans may be obtained at other time points if clinically indicated to confirm a clinical diagnosis of disease progression based on signs and symptoms.

Inclusion Criteria

- a) Written informed consent in accordance with institutional guidelines. If required by local law, candidates must also authorize the release and use of protected health information (PHI);
- b) Female subjects age 18 years or older;
- c) Histological diagnosis of squamous cell carcinoma, adenocarcinoma or adenosquamous cell carcinoma of the cervix. Not accepted are small cell, clear cell and other rare variants of the classical adenocarcinoma;
- d) Histologically confirmed, Stage IB-IVB, invasive cervical carcinoma associated with HPV-16 and/or HPV-18 and meeting the following eligibility criteria for either Cohort 1 or Cohort 2;

Inclusion Criteria Contd.

1. Cohort 1
    - Newly diagnosed inoperable cervical cancer treated with chemoradiation therapy with curative intent and a life expectancy of at least 12 months as assessed by the investigator.
      - No CNS/spinal metastases
    - Able to initiate study treatment (Day 0) within 2 weeks of completion of last chemoradiation treatment;
      - Platinum based treatment (alone or in combination with other drugs); 5 weekly courses of Cisplatin 40 mg/m^2 completed within 10 weeks of its initiation
      - Standard radiation therapy (external beam and brachytherapy); completed within 10 weeks of its initiation
      - Brachytherapy; must be the last treatment if the subject is receiving sequential brachytherapy following the chemoradiation therapy
  2. Cohort 2
    - Persistent and/or recurrent cervical cancer
      - No CNS/spinal metastases
    - Able to initiate study treatment (Day 0) at least 2 weeks after but no more than 4 weeks after completion of salvage therapy (If in the investigators opinion, there are no additional salvage therapy options, the subject may be enrolled in Cohort 2 without having received salvage therapy immediately prior to enrollment.)
    - Subject has a life expectancy of at least 12 months as assessed by the investigator
- e) ECG with no clinically significant findings as assessed by the investigator performed within 30 days of signing the informed consent form (ICF);
  - f) Chemistry, liver function tests, renal function, total creatine phosphokinase (CPK) and hematology lab results must be ≤ Grade 1 at the time of screening, in accordance with the CTCAE v4.03;
  - g) Eastern Cooperative Oncology Group (ECOG) Performance status of ≤ 1;
  - h) Adequate venous access for repeated blood sampling according to study schedule;
  - i) Women of child-bearing potential must have a negative serum pregnancy test and agree to remain sexually abstinent, have a partner who is sterile (i.e., vasectomy), or use two medically effective methods of contraception (e.g., oral contraception, barrier methods, spermicide, intrauterine device (IUD)). This requirement should be followed from screening through 24 weeks after last study treatment/EP. Whole pelvis external beam radiation therapy (EBRT) followed by intracavitary (IC) therapy for cervical cancer is considered to be an irreversible form of contraception;
  - j) Able and willing to comply with all study procedures.

Exclusion Criteria:

- a) Pregnancy or breastfeeding;
- b) History of previous therapeutic HPV vaccination (individuals who have been immunized with licensed prophylactic HPV vaccines (e.g. Gardasil®, Cervarix®) are not excluded);
- c) Prior exposure to an investigational agent or device within 30 days of signing the ICF. Of note, the subject may participate in observational studies;
- d) Positive serological test for human immunodeficiency virus (HIV), Hepatitis B or Hepatitis C or history of HIV infection, Hepatitis B or Hepatitis C (women with cured HCV will be allowed; subject must have had an serologic test performed within 12 months of informed consent);
- e) Prior major surgery within 4 weeks of first study treatment/EP from which the subject has not yet recovered to baseline;
- f) High medical risks because of non-malignant systemic disease or with active uncontrolled infection;
- g) Current malignancies at other sites, with the exception of adequately treated basal or squamous cell carcinoma of the skin;
  - Cancer survivors, who have undergone curative therapy for a prior malignancy, have no evidence of that disease for five years and are deemed at low risk for recurrence, are eligible for the study;
- h) Congestive heart failure or prior history of New York Heart Association (NYHA) class III/ IV cardiac disease (refer to Appendix 8);
- i) Any concurrent condition requiring the continued use of systemic or topical steroids at or near the injection site, excluding non-systemic (e.g. inhaled and eye drop-containing) corticosteroids or the use of other immunosuppressive agents. All other corticosteroids must be discontinued > 4 weeks prior to Day 0 of study product administration;
- j) Any cardiac pre-excitation syndromes (such as Wolff-Parkinson-White);
- k) History of seizures (unless seizure free for 5 years);
- l) Less than two acceptable sites exist for IM injection and EP between use of the deltoid and lateral quadriceps muscles. A site for injection/EP is not acceptable if there are tattoos or scars within 2 cm of the injection/EP site or if there is implanted metal within the same limb. Any device implanted in the chest (e.g., cardiac pacemaker or defibrillator) excludes the use of the deltoid muscle on the same side of the body;
- m) Administration of any non-study related vaccine within 2 weeks of Day 0;
- n) Active drug or alcohol use or dependence that, in the opinion of the investigator, would interfere with adherence to study requirements;
- o) Imprisonment or compulsory detainment (involuntary incarceration) for treatment of either a psychiatric or physical (i.e. infectious disease) illness;
- p) History of immunosuppressive or autoimmune disease;
- q) Any other illnesses or conditions that in the opinion of the investigator may affect the safety of the subject or limit the evaluation of a subject or any study endpoint.

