### **Primary Safety Endpoints:**

1. Incidence of adverse events (all, severe [graded per CTCAE v4.03], unexpected, serious) classified by system organ class (SOC), preferred term, severity, and relationship to study medication and schedule
2. Injection site reactions including pain, tenderness, erythema and induration at administration site
3. Rates of acute gastrointestinal, genitourinary, or other chemoradiation side effects above the expected, graded per Acute Radiation Morbidity Scoring Criteria (RTOG)
4. Changes in laboratory parameters from baseline

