### 6.1 Procedure by Visit

#### 6.1.1 Screening Evaluations

Subjects who consent to participate in the study will be eligible for screening and will have a tumor biopsy sample (i.e. unstained slides) sent to laboratory for HPV assessment that will be done either by ISH or PCR. If a subject has documented evidence of HPV-16 and/or HPV-18 infection results from cervical specimen obtained prior to anti-cancer treatment, then those results will be acceptable. If applicable, ThinPrep™ sample should also be sent simultaneously to the central lab for HPV assessment by PCR. Another cervical biopsy should be collected at screening if residual tissue is not available for additional assessment. The screening assessments, if required may be done in two parts. The first part will consist of consenting the subject and collecting cervical biopsy samples for HPV assessment. The second part of the visit will consist of performing the remaining screening assessment.

Subjects in Cohort 1 can be screened either prior to initiation of chemoradiation or during chemoradiation. Subjects should be screened and enrolled such that their first study treatment (Day 0) will be delivered within 2 weeks of completing their chemoradiation therapy.

Subjects in Cohort 2 can be screened at any time prior to the date of their first study treatment. Subjects should be screened and enrolled such that their first study treatment (Day 0) is no sooner than 2 weeks and no later than 4 weeks after completing the salvage therapy.

The following evaluations will be performed at **screening** visit prior to Day 0:

- Signed informed consent
- Histologic diagnosis of cervical cancer
- Collect demographic information
- Determination of eligibility per inclusion and exclusion criteria
- Medical and CIN/cancer history
- Medical/clinical assessment
- Adverse event (AE)/Serious adverse event (SAE) assessment
- Determine disease status
- Concomitant medications review
- Assessment of systemic reaction/toxicity/side effects of standard (chemoradiation) therapy (only if subject is screened during chemoradiation therapy)

- Full physical exam to include complete gynecological exam and ECOG performance status
- Vital Signs (including body temperature, respiratory rate, blood pressure, heart rate and height/weight)
- 12-lead ECG
- HPV assessment
- Tumor biopsy collection (required only if residual tissue or unstained slides are not available at screening)
- ThinPrep™ sample for HPV testing (if applicable)

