#### **6.2.4.9 Laboratory Evaluations**

At screening, blood samples will be collected for serum chemistry and hematology. A urine sample will also be obtained to determine eligibility. At other visits, blood samples will be collected as specified in Table 1 - Schedule of Events. All labs for Day 0 and those associated with any treatment visit should be collected no more than 48 hours prior to treatment and reviewed/evaluated by the PI prior to treatment. Approximately 4 cups of blood will be drawn from each subject during the entire duration of the study.

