#### **6.5 Assessment of Laboratory Abnormalities**

Investigators may use clinical judgment to enroll subjects with isolated Grade 1 abnormalities in screening CBC, serum chemistry or CPK values if there is no indication of disease process in the remainder of the history and physical examination.

Blood will be drawn for serum chemistry, hematology and serology assessments as well as pregnancy testing at screening for inclusion into the study as listed in sections 6.2.4.8 and 6.2.4.9.

Urinalysis will be performed at screening to fulfill eligibility criteria. CPK will be performed at Screening and Week 16.

Complete blood count with differential and serum chemistry will be performed at each study treatment/EP and Week 16.

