- courses of cisplatin, renal function must return to normal before another dose can be given.
- b. Ototoxicity: Ototoxicity has been observed in up to 31% of patients treated with a single dose of cisplatin 50 mg/m^2. It is manifested by tinnitus and/or hearing loss in the high frequency range. Deafness has been reported rarely.
  - c. Hematologic Toxicity: Myelosuppression occurs in 25-30% of patients treated with cisplatin. Nadirs in circulating platelets and leukocytes occur between Days 18 and 23 with most patients recovering by Day 39. Thrombocytopenia, anemia, neutropenia, and fever are also possible adverse events.
  - d. Gastrointestinal Toxicity: Marked nausea and vomiting occur in almost all patients treated with cisplatin. Diarrhea and anorexia have also been reported.
  - e. Neurotoxicity: Neurotoxicity usually characterized by peripheral neuropathies, has been reported. Neuropathy usually occurs after prolonged therapy (4 to 7 months); however, symptoms have been reported after a single dose. Muscle cramps, loss of taste, seizures, autonomic neuropathy, dorsal column myelopathy, and Lhermitte's sign have also been reported.
  - f. Ocular Toxicity: Optic neuritis, papilledema, and cerebral blindness have been reported infrequently in patients receiving standard recommended doses of cisplatin. Blurred vision and altered color perception have been reported after the use of regimens with higher doses of cisplatin or greater dose frequency than those recommended in the package insert.
  - g. Anaphylactic-like Reactions: Anaphylactic-like reactions have occasionally been reported in patients previously exposed to cisplatin. Symptoms include facial edema, wheezing, tachycardia, and hypotension.
  - h. Hepatotoxicity: Transient elevations in liver enzymes, especially SGOT (AST), and bilirubin, have been reported.
  - i. Other Toxicities: Other infrequent toxicities that have been reported include cardiac abnormalities, hiccups, elevated serum amylase, rash, alopecia, malaise, and asthenia. Rare cases of local soft tissue adverse events have occurred.
- V. Mechanism of Action: Primarily causes inhibition of DNA synthesis and, to a lesser degree, inhibition of RNA and protein; it has not been shown to be cell cycle specific.

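### CPK has no Day 0 value, so its change from baseline in primary endpoint 4 can take in the whole of chemoradiation; for the other laboratory tests the baseline draw is not stated

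*Combined protocol and SAP*

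**What the plan says.** The fourth primary safety endpoint (Synopsis and Section 3) reads "Changes in laboratory parameters from baseline". Neither the endpoint nor Section 8.2 defines baseline, and Section 8.2 describes no analysis of laboratory change.

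Section 6.5 gives two sampling schedules:

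- For CPK: "CPK will be performed at Screening and Week 16". Table 1 agrees, and the Day 0 list in Section 6.1.2 has no CPK. Section 6.1.1 lists the screening sample as the baseline CPK.
- For the other bloods: "Complete blood count with differential and serum chemistry will be performed at each study treatment/EP and Week 16". Section 6.2.4.9 has treatment-visit samples taken no more than 48 hours before dosing.

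Section 6.1.1 sets the screening windows. For Cohort 1: "Subjects in Cohort 1 can be screened either prior to initiation of chemoradiation or during chemoradiation". For Cohort 2: "Subjects in Cohort 2 can be screened at any time prior to the date of their first study treatment". The baseline PET/CT must fall within 4 weeks of Day 0; no such limit is given for the laboratory tests.

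Inclusion criterion f (Synopsis and Section 4.1) covers chemistry, liver and renal function, CPK and hematology, and requires that "hematology lab results must be ≤ Grade 1 at the time of screening". Section 6.1.2 has eligibility determined again on Day 0. Section 6.2.4.9 has the Day 0 results "reviewed/evaluated by the PI prior to treatment", with no grade attached.

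**The concern.** A change from baseline describes the treatment period only if baseline sits next to the first dose. For CPK it need not. In Cohort 1 the screening sample can come before the entire chemoradiation course; in Cohort 2 it can come before salvage therapy. Whatever happens to CPK in that time is added to whatever happens after electroporation into muscle, and the data cannot separate the two. CPK is not incidental here: Section 1.3.1 reports post-electroporation CPK as a safety finding from HPV-001.

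For counts and chemistry the sample exists but its role is undefined. A baseline before chemoradiation would show residual cisplatin toxicity as change on study. A baseline during chemoradiation would show recovery as improvement and could hide a treatment effect. Section 7.2.1 also defines laboratory adverse events as new or worse than the baseline condition, so the choice reaches endpoint 1. With about 10 subjects, one or two misread changes would alter the tables visibly.

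**Working it through.** **1. The plan's own figures.** The plan gives no figure on this point. The Section 8.1 figures reproduce: 1 − 0.77^10 = 0.927 (stated as about 92%), and the exact two-sided 95% upper limit for 0 of 10 is 1 − 0.025^(1/10) = 0.308 (stated as below 31%). Neither depends on the choice of baseline.

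**2. Length of the CPK interval, Cohort 1.** Inputs: radiation completed within 10 weeks and Day 0 within 2 weeks of the last chemoradiation treatment (criterion d); Week 16 visit ±1 week (Table 1, footnote a).

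- Shortest (screened at the end of chemoradiation, Day 0 at once, early visit): 0 + 0 + 16 − 1 = 15 weeks.
- Long case (screened just before a 10-week course, 2-week gap, late visit): 10 + 2 + 16 + 1 = 29 weeks. No limit is set on how long before chemoradiation screening may occur, so 29 is not a maximum.
- In the long case 12 of the 29 weeks (41%) come before the first dose.

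Cohort 2 has no stated upper limit at all. If screening precedes salvage therapy, the interval includes that course plus the 2 to 4 weeks before Day 0.

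**3. What the reported CPK change contains.** Write S, D and W for the Screening, Day 0 and Week 16 values:

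W − S = (D − S) + (W − D).

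Only W − D belongs to the study-treatment period. D is never measured, so the split cannot be made. With D measured, the interval becomes 16 ± 1 = 15 to 17 weeks for every subject, whenever she was screened.

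**4. Counts and chemistry.** Both S and D exist. Section 6.7 does not settle which is baseline: for immunology samples it counts Screening and Day 0 together as baseline.

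**5. How clean a Day 0 baseline would be.** Appendix 3 says of cisplatin: "Nadirs in circulating platelets and leukocytes occur between Days 18 and 23 with most patients recovering by Day 39". Assumptions: those days count from the last dose; cisplatin starts on radiation day 1; radiation ends between day 40 (assumed) and day 70 (10 × 7). Appendix 3 gives five cycles in one place and six weekly infusions in another, which must be reconciled; both are carried here. The last dose falls on day 1 + 4 × 7 = 29 or day 1 + 5 × 7 = 36.

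- Earliest Day 0: 40 + 0 − 36 = 4 days after the last cisplatin, so Day 39 recovery lies 39 − 4 = 35 days after Day 0.
- Latest Day 0: 70 + 14 − 29 = 55 days after, so Day 39 recovery lies 55 − 39 = 16 days before Day 0.

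A Day 0 baseline may therefore sit near a nadir or well past recovery.

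**6. Criterion f against Day 0.** A woman screened before chemoradiation meets or fails f on untreated blood. Screened during it, she is judged on blood drawn under treatment. The Day 0 eligibility check does not remove the difference, because f itself points back to screening. The same holds in Cohort 2 for screening before or after salvage therapy.

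**The case against.** The other side has several good points.

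- Counts and chemistry, where Appendix 3 describes marrow, renal and hepatic effects of cisplatin, are redrawn within 48 hours before the first dose, and an analyst would probably use that value.
- Carry-over is partly handled elsewhere. RTOG scoring, which includes blood counts (Appendix 5), is done immediately before the first dose. Chemoradiation toxicity has its own reporting period through Week 4 (Section 9.3.1). Pre-existing conditions count as adverse events only if they worsen (Section 7.1.1). Exclusion q gives the investigator discretion at Day 0.
- Screening may be done in two parts, so the laboratory tests can come late. The long interval is permitted, not required, and the documents give no frequency for it.
- CPK was unremarkable after electroporation in HPV-001, so sparse sampling is defensible. A Day 0 CPK would still leave only one post-dose value, nominally 4 weeks after dose 4.

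These points stand, and they limit the finding. None of them supplies a CPK value near the first dose: the RTOG scale has no CPK item. Nor do they say which draw is baseline for the other tests.

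A reader might infer something stronger: that because f is tied to screening, cisplatin carry-over enters endpoint 4. The documents do not support this. An entry criterion does not set an endpoint's baseline, and Appendix 3 lists no cisplatin effect on CPK. The CPK problem is one of interval and attribution, not demonstrated contamination. A reader might also turn the 23% rate in Section 8.1 into a share of women who would fail f, or who reach Day 0 with toxicity. It is a per-patient rate of grade 3 or 4 hematologic toxicity, not the grade on one draw, and the number of women screened early is unknown. No such percentage can be derived.

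**Conclusion.** The point holds for CPK as a matter of schedule. The only CPK contrast in a primary endpoint runs from a screening sample to Week 16, over about 15 to 29 or more weeks, and can include all of chemoradiation. It cannot be read as an effect of INO-3112/EP. The 15 and 29 weeks rest only on the stated limits and visit windows; how many women would fall at the long end is unknown.

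For counts and chemistry the defect is smaller: the right sample is collected, and the plan omits to say that it is the baseline. The dependence of criterion f on screening date is a separate inconsistency, present in both cohorts, for the sponsor to reconcile. No view is taken here on which draw or grade should apply.

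The study is descriptive and single-arm, so this does not affect the sample size statement or any test. Even with a Day 0 value, a CPK change would describe the treatment period rather than prove cause. The change is worth making because it repairs a primary-endpoint contrast at very little cost.

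**What to change.** 1. **Table 1, Sections 6.1.2 and 6.5:** add CPK to the Day 0 pre-dose sample, as the CPK baseline for endpoint 4.
2. **Endpoint 4 and Section 8.2:** state that baseline for every laboratory parameter is the Day 0 pre-dose value. Tabulate post-dose grades as shifts from the Day 0 grade, and show Screening values separately as pre-study information.
3. **Interpretation:** note in Section 8.2 that Day 0 may precede full recovery from cisplatin, so later recovery can appear as improvement and can mask a fall caused by study treatment.
4. **Criterion f, the Day 0 eligibility determination (Section 6.1.2) and the Day 0 laboratory review (Section 6.2.4.9):** the sponsor must reconcile these passages for both cohorts. No draw or threshold is proposed.

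The cost is one extra analyte per subject, about 10 in all, on blood already drawn, plus the wording changes. Table 1 (footnote o) wants Day 0 results available before treatment, so the sponsor should state whether that applies to the added CPK or whether it serves only as the endpoint baseline. The remaining drawbacks are the incomplete removal of carry-over in item 3 and the single post-dose CPK value, which this change does not address.
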